#### 8.3.5 ADVERSE EVENT REPORTING

This study will follow the standard Institutional Review Boards of the University of Michigan Medical School (IRBMED) reporting schedule for AEs. Refer to

[https://az.research.umich.edu/sites/default/files/Adverse%20Event%20Reporting%20Guidelines%20for%20INTERNAL%20AEs%20Occurring%20at%20UM\\_1152018%20OUTWARD%20facing.pdf](https://az.research.umich.edu/sites/default/files/Adverse%20Event%20Reporting%20Guidelines%20for%20INTERNAL%20AEs%20Occurring%20at%20UM_1152018%20OUTWARD%20facing.pdf) for a printable version.

Briefly, this reporting schedule precludes reporting to IRBMED all expected non-serious events regardless of relatedness. These events will be recorded in the study record and evaluated for occurrence rates. If any event seems to occur in greater numbers than expected or are more severe than previously known, we will file a report with IRBMED and DSMB.

---

#### 8.3.6 SERIOUS ADVERSE EVENT REPORTING

- All SAEs will be reviewed and evaluated by the PI and [name], and reported to the following groups: DSMB, IRBMED, and the Sponsor
- SAEs or new clinical findings which meet the reporting requirements under the Federal Food, Drug, and Cosmetic Act and/or the Code of Federal Regulations will be reported to the FDA.
  - Any unexpected fatal or life-threatening suspected adverse reaction to the study product will be reported no later than 7 calendar days after initial receipt of the information.
  - Any (1) serious, unexpected suspected adverse reactions, (2) findings from other clinical, animal, or in-vitro studies that suggest significant human risk, and (3) a clinically important increase in the rate of a serious suspected adverse reaction will be reported no later than 15 calendar days after determining that the information qualifies for reporting.
- The study team will notify the participant's treating physician of any study product-related SAE.

- All SAEs will be followed until satisfactory resolution or until [name] and/or the participant's treating physician deem the event to be chronic or that the participant is stable.
- The PI and study team will notify all parties of any unexpected fatal or life-threatening suspected adverse reaction to the study product as soon as possible, but no later than 7 days after becoming aware of the event.

---

### 8.3.7 REPORTING EVENTS TO PARTICIPANTS

In general, the occurrence of adverse events throughout the study will not be reported back to the participants. Exceptions to this general policy include:

- SAEs that are related to the study product.
- Findings of the DSMB related to patterns of AE/SAE occurrence that might impact one's decision to continue participation.

Phone calls will be the primary method of communication in these cases and will be documented in the study record.

---

### 8.3.8 EVENTS OF SPECIAL INTEREST

We will document any challenges, difficulties or complaints associated with the following:

- Delivery of study product.
- Stability of study product.
- Usability of study product and supplies.

---

### 8.3.9 REPORTING OF PREGNANCY

Pregnancy is not considered an adverse event, but it is an exclusion criterion for the study. Individuals reporting a new pregnancy will discontinue their study intervention and will be withdrawn from the study.

---

## 8.4 UNANTICIPATED PROBLEMS

---

### 8.4.1 DEFINITION OF UNANTICIPATED PROBLEMS (UP)

We will use the IRBMED criteria to determine the occurrence of an unanticipated problem. All three criteria must be met for an occurrence to be deemed an UP. More guidance from IRBMED regarding UPs can be found at the following link: <https://research.medicine.umich.edu/office-research/institutional-review-boards-irbmmed/guidance/adverse-events-aes-other-reportable-information-and-occurrences-oriost-and-other-required-reporting/unanticipated-problems-involving-risks-subjects-or-others>

1. The occurrence is **unexpected** in terms of nature, severity or frequency relative to what is written in this protocol document and IRBMED application *and* considering the characteristics of the study population.
2. The occurrence is **related or possibly related** to participation in this study with "possibly related" defined as there being a "reasonable possibility that the incidence, experience, or outcome may have been caused by the procedures.
3. Suggests that participants or others are **at greater risk than previously thought**.

---

#### 8.4.2 UNANTICIPATED PROBLEM REPORTING

- Unanticipated problems that are also SAEs will follow the SAE reporting schedule and guidelines.
- Unanticipated problems that are not associated with an SAE will be reported to the DSMB, IRBMED, the Sponsor within 14 days of the study team becoming aware of the problem.
- Reports will include the following information:
  - Description of the problem, i.e., what occurred, how it occurred, any outcome, etc.
  - Discussion of why the event is considered an unanticipated problem.
  - A corrective action plan.

---

#### 8.4.3 REPORTING UNANTICIPATED PROBLEMS TO PARTICIPANTS

Participants will be notified forthwith about problems that directly impact their current risk level or potentially impact their decision to remain enrolled in the study. Examples of problems that would require prompt reporting:

- Contamination of study product.
- Problems leading to injury or illness related to study supplies (e.g. catheter tips or syringes).
- Breach of confidentiality.

Phone calls will be the primary method of communication in these cases, and will be documented in the study record.

## 9 STATISTICAL CONSIDERATIONS

### 9.1 STATISTICAL HYPOTHESES

Our primary hypothesis (H1) is that during the six-month treatment period, incidence of UTIs will be significantly lower than it had been during the six months prior to the treatment period. Our Secondary Hypothesis (H2) states that there will be significantly fewer bladder and bowel complications as reported on the various patient-reported outcome measures at the end of treatment than there had been on the baseline interview, just prior to the start of treatment.

Our tertiary hypotheses (H3 and H4) center on health-related quality of life and community participation. We expect that at the end of the treatment period, QOL will be significantly higher than it had been at the time of the baseline interview, prior to treatment (H3). Similarly, we expect that at the end of the treatment period, community participation will be significantly better than it had been at the time of the baseline interview (H4).

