## 1 PROTOCOL SUMMARY

### 1.1 SYNOPSIS

Title:	The Effect of Gentamicin Intravesical Instillations on Decreasing Urinary Tract Infections in Patients with Neurogenic Bladder after SCI: A Clinical Trial
Study Description:	A trial to assess the efficacy of intravesical gentamicin on the occurrence rate of urinary tract infections (UTIs) and bladder complications in patients after SCI, and to assess its effectiveness in promoting overall QOL, community living, and participation.
Objectives:	
Primary Objective: Evaluate efficacy of intravesical gentamicin in reducing the number of urinary tract infections during a six-month period.
 
Secondary Objectives: Examine the effectiveness of gentamicin in decreasing associated bladder and bowel complications.
 
Tertiary Objective: Examine the effect of gentamicin on improving health-related quality of life and community participation.

Endpoints:	
Primary Endpoint: Number of UTIs
 
Secondary Endpoints: Number of complications
 
Tertiary Endpoints: Quality of life and participation scores

Study Population:	Adults with a traumatic or non-traumatic SCI with neurogenic bladder and recurrent urinary tract infections
Phase:	Phase 2/3
Description of Sites/Facilities Enrolling Participants:	Michigan Medicine (academic medical institution in southeastern Michigan affiliated with the University of Michigan)
Participants:	Department of Physical Medicine and Rehabilitation Department of Urology
Description of Study Intervention:	Intravesical gentamicin + saline instillations
Study Duration:	12 months
Intervention Duration:	6 months

 Throughout this document, six months refers to 180 days.

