### 3 OBJECTIVES AND ENDPOINTS

OBJECTIVES	ENDPOINTS	JUSTIFICATION FOR ENDPOINTS
Primary		
The use of intravesical gentamicin reduces the incidence of UTIs during treatment	A reduction in the count of UTIs during the six months of treatment	Allows for verification of reduced UTIs during the intervention. UTIs are associated with major medical, psychological, social and economic consequences
Secondary		
Gentamicin treatment will decrease self-reported bladder complications	A reduction in scores of the Neurogenic Bladder Symptom Severity at six months of gentamicin use.	Allows for validated self-assessment of bladder symptoms in patients with SCI following the intervention.
Gentamicin treatment will decrease self-reported bowel complications	A reduction in scores of the Neurogenic Bowel Dysfunction at six months	Allows for a validated self-assessment of bowel dysfunction severity in patients with SCI following the interventions
Tertiary/Exploratory (other pre-specified analyses)		
The use of intravesical gentamicin will enhance overall quality of life	An increase in SF-Qualiveen scores at six months of gentamicin use	UTIs, associated bladder and bowel complications contribute to reduced QOL in patients with SCI manifesting in negative affect and psychological functioning
The use of intravesical gentamicin will enhance quality of life by decreasing bladder management difficulties	An improvement in SCI-QOL: Bladder Management scores at six months.	
The use of intravesical gentamicin will enhance quality of life by decreasing bladder complications	An improvement in SCI-QOL: Bladder Complications scores at six months.	
The use of intravesical gentamicin will enhance quality of life by decreasing bowel management difficulties	An improvement in SCI-QOL: Bowel Management Difficulties scores at six months.	
The use of intravesical gentamicin will increase overall community participation	An improvement in Community Participation Indicators Scale scores at six months.	Repeated UTIs, associated bladder and bowel complications negatively impact patients' interactions with their social environments
The use of intravesical gentamicin will increase subject's satisfaction with roles and activities scale	An improvement in SCI-QOL: Satisfaction with roles and activities scale scores at six months.	

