## 9.4 STATISTICAL ANALYSES

### 9.4.1 GENERAL APPROACH

All data will be examined for completeness and outliers before hypothesis testing. Categorical data will be summarized in terms of frequencies, presented as n (%), and continuous data will be summarized in terms of means (standard deviations). Participant demographics and clinical status will be evaluated using descriptive statistics. These analyses will be conducted after all data has been collected. All efforts will be made to recruit a balanced sample representative of persons with SCI/D. Missing data will be handled using common statistical methods such as multiple imputation and the estimation maximization approach.

All statistical procedures will be run using either SPSS or the statistical package R. Statistical significance will be set at  $p < 0.05$  for group comparisons and all models.

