### 9.4.3 ANALYSIS OF THE SECONDARY AND TERTIARY ENDPOINT(S)

To assess the impact of the study intervention on our Secondary Endpoint, bladder, and bowel complications (Hypothesis 2), and Tertiary Endpoints, QOL (Hypothesis 3), and Participation (Hypothesis 4), a similar analytic approach will be used as was used for Hypothesis 1. The outcomes for these hypotheses are all continuous and therefore paired t tests or GLMM will be used. Our plan for handling missing data across all study analyses will include the use of common statistical methods to handle missing data such as multiple imputation and the estimation maximization approach. As appropriate, we may employ sensitivity analysis to assess the effect of data that is not missing at random such as when participants stop using the research treatment but continue to be willing to participate in the study's assessments.

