**Statistical Analysis Plan**

**6/23/2023**

### **Statistical Analysis Plan**

All data were examined for completeness and outliers before hypothesis testing. Categorical data was summarized in terms of frequencies, presented as n (%), and continuous data will be summarized in terms of means (standard deviations). Participant demographics and clinical status were evaluated using descriptive statistics. All efforts were made to recruit a balanced sample representative of persons with SCI/D. Statistical significance was set at  $p < 0.05$  for group comparisons with a 95% confidence interval.

To test for significant differences in the incidence of UTIs across periods (six months pre-treatment, six-month treatment, one-month post-treatment, six months post-treatment) an incidence rate per person month was determined by comparing the total number of UTIs in relation to duration, reflecting all participants across six months. The incidence rate ratio was determined by comparing the different timepoint ratios in relation to pre-treatment ratio. Confidence intervals and p values were calculated for rates and rate ratios. This approach analytical was used to satisfy small sample size calculations, as appropriate with count outcomes data (Hypothesis 1). To assess the impact of the study intervention on our Secondary Endpoint, bladder, and bowel complications (Hypothesis 2), and Tertiary Endpoints, QOL (Hypothesis 3), paired t tests were used to test differences in scores across survey measures.

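### Hypothesis 2 is defined in three ways that do not match, and the loosest would let about five bladder or bowel scales support it, each at p<0.05 with no success rule

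*Protocol*

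**What the plan says.** The documents describe H2 and its endpoint in several places:

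- **Protocol 1.1 (synopsis):** a count, "Secondary Endpoints: Number of complications". The hypotheses in 4.1 also speak of a number of bladder and bowel complications, lower over the treatment period than reported at the baseline interview.
- **Protocol 3:** two scores, one per objective. For bladder it is "A reduction in scores of the Neurogenic Bladder Symptom Severity at six months of gentamicin use"; for bowel it is a reduction in the Neurogenic Bowel Dysfunction score at six months. The other six scales are tertiary. One of them has the endpoint "An improvement in SCI-QOL: Bladder Complications scores at six months" and is placed under quality of life.
- **Protocol 9.1:** an open set. H2 is that "there will be significantly fewer bladder and bowel complications as reported on the various patient-reported outcome measures at the end of treatment", compared with the baseline interview.
- **Protocol 9.4.3:** "The outcomes for these hypotheses are all continuous and therefore paired t tests or GLMM will be used".
- **Protocol 9.4.1:** the 0.05 threshold applies "for group comparisons and all models".
- **SAP:** for H2 and H3, "paired t tests were used to test differences in scores across survey measures". No scale is assigned to either hypothesis, and H4 is not mentioned.

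Eight scales are given at baseline and at the end of treatment (Protocol 1.3 and 8.1). Neither document contains a hierarchy, a multiplicity rule, or a statement of whether H2 needs bladder and bowel results together or either alone.

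**The concern.** A reader of the final report cannot tell from the plan which result decides H2. The count in 1.1 and 4.1 cannot be that result. Protocol 8.1 records bladder and bowel symptoms, and 8.3.4 collects adverse events from consent onward, but neither is described as a complication count over matched periods before and during treatment. The instruments measured twice are scales.

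If 9.1 is taken at its word, the secondary claim could rest on whichever bladder or bowel scale reaches p<0.05. The SAP, which ought to close the question, leaves it open. The study is a single-group, open-label, before-after comparison using self-reported scales, so fixing the deciding measures in advance is one of the few protections these results have. What is at stake is how the secondary and tertiary results may be worded; the primary UTI comparison does not depend on it.

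**Working it through.** **1. The definitions side by side**

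| Place | What H2 is | When |
|---|---|---|
| Protocol 1.1 | count of complications | not stated |
| Protocol 4.1 | count of complications | over the treatment period |
| Protocol 3 | two named scores | six months |
| Protocol 9.1 | unnamed set of patient-reported measures | end of treatment |
| Protocol 9.4.3 | continuous outcomes | not stated |
| SAP | survey scores, none assigned to H2 | not stated |

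A count and a continuous score are different endpoints, and a whole period is a different target from a single time point. Section 3 and 9.4.3 are compatible with each other. The count wording fits neither.

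**2. How many scales the 9.1 wording can reach**

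Of the eight scales, five name the bladder or bowel: NBSS, NBD, and the SCI-QOL scales Bladder Management Difficulties, Bladder Complications and Bowel Management Difficulties. SF-Qualiveen, described in 8.1 as a measure for urinary disorders, would make six. The remaining two, Community Participation Indicators and Satisfaction with Social Roles and Activities, serve H4. The H2 family is therefore two scales under section 3 and about five, at most six, under 9.1.

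**3. Chance of a false claim**

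The plan gives no figure of its own for H2. Its only sample-size figure, 15 completers for 80% power, belongs to the primary hypothesis. I use it here only as n.

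Inputs: per-test level 0.05 (9.4.1); n=15 (9.2); paired t tests (9.4.3 and SAP). Sidedness is not stated, so two-sided tests are assumed. With k independent scales and no true change:

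- at least one significant result in either direction: 1 − 0.95^k
- at least one significant result in the direction of benefit: 1 − 0.975^k

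For k=2: 1 − 0.95² = 9.8% and 1 − 0.975² = 4.9%. For k=5: 1 − 0.95⁵ = 22.6% and 1 − 0.975⁵ = 11.9%. A single two-sided test gives 2.5% in the direction of benefit.

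The documents give no correlation between scales. The correlated columns are simulated paired t tests (n=15, 60,000 runs each) at assumed equal correlations of 0.5 and 0.9.

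| Scales | Benefit, independent | Benefit, 0.5 | Benefit, 0.9 | Either direction, independent | Either, 0.5 | Either, 0.9 |
|---|---|---|---|---|---|---|
| 2 | 4.9% | 4.7% | 3.6% | 9.8% | 9.4% | 7.1% |
| 5 | 11.9% | 9.4% | 5.4% | 22.6% | 18.8% | 10.8% |
| 6 | 14.1% | 10.8% | 5.6% | 26.5% | 21.4% | 11.2% |
| 8 | 18.3% | 13.0% | 6.3% | 33.7% | 25.8% | 12.6% |

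The eight-scale row is the chance of some significant result among all secondary and tertiary scales together. It is not the chance of a false H2 claim. If the tests were one-sided at 0.05 in the direction of benefit, the benefit figures for independent scales would be 1 − 0.95^k, the same as the independent either-direction column.

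**4. Power under a success rule**

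A standardised paired change of 0.778 has 80% power at n=15 and two-sided 0.05. At 0.025, the first Holm step for two scores, the same effect has 69.1%. If both scores must succeed and each has 80%, joint power is 0.80 × 0.80 = 64% when the scores are uncorrelated, and higher with positive correlation. The effect 0.778 is a reference value; the plan states no effect for H2.

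**The case against.** The strongest reply is that section 3 is where endpoints are defined. It gives each secondary objective one named score and labels everything else tertiary. On that reading there are two tests, and the false-benefit chance with two-sided tests is about 5%. The five-scale family is assembled from scale names. Two of its members measure management difficulties rather than complications, and section 3 expressly files the SCI-QOL Bladder Complications scale under quality of life. The wording of H2 can also be read as requiring bladder and bowel together, in which case no adjustment is needed.

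Much of this stands. A reader might infer that fewer complications could be claimed on whichever of all eight scales succeeds, with a chance of about one in three. The documents do not support that. Section 3 limits the secondary objective to two scores, 9.1 speaks only of bladder and bowel, and the two participation scales serve H4. A reader might also take 22.6% as the risk of a false claim of benefit, but with two-sided tests that figure includes apparent worsening. Nor do the documents make any one adjustment compulsory for two secondary endpoints; statisticians differ on that.

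What the reply does not remove is the conflict itself. Protocol 9.1 is the statistical hypothesis and it reopens the list. The schedule of activities calls all eight scales quality-of-life measures, including the two that section 3 assigns to H2. The SAP assigns none. No text says whether both scores or either one decides H2.

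**Conclusion.** The concern holds as one of inconsistent definition. H2 is a count that is not collected, two named scores, or an open set of scales, at two differently described times, with no success rule. Moving from the section 3 definition to the 9.1 wording raises the chance of at least one false finding of benefit from about 4.9% to 11.9% (9.8% to 22.6% counting either direction). These figures assume no true change, two-sided tests at 0.05 and independent scales. They fall with correlation, to 3.6% and 5.4% for benefit at an assumed 0.9. The count of five rests on scale names, because the documents give no item content. The defect limits what may be claimed from the secondary and tertiary results and should be corrected; the primary UTI test is untouched.

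**What to change.** 1. In Protocol 1.1, 4.1 and 9.1 and in the SAP, define H2 as section 3 does: change from baseline to six months in the NBSS total and the NBD total. Say explicitly that totals are meant, since 8.1 describes the NBSS as three domains plus an overall quality-of-life item. Use the same instrument name in section 3 and 8.1.
2. Replace the count wording in 1.1 and 4.1, and the reference to fewer complications in 9.1, with lower symptom scores.
3. State the success rule. If H2 needs both scores, test each at 0.05 with no adjustment. If either is enough, use Holm or a fixed sequence at an overall 0.05. State sidedness.
4. Report the six tertiary scales as mean change with 95% confidence interval, and not as support for H2.

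No new data are needed. The cost is some power, depending on the rule. With Holm, the first step at 0.025 has about 69% power for an effect that has 80% at 0.05 with n=15; this is a lower bound for either score, because the second step is at 0.05. Requiring both gives about 64% in the uncorrelated case shown above. A fixed sequence costs the first score nothing, but the second can be claimed only if the first succeeds. The SAP is written in the past tense; if the analyses have been done, apply the same rule to the reporting and disclose that it was set afterwards.

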### 9.2 SAMPLE SIZE DETERMINATION

Power calculations were conducted based on the **primary hypothesis that incidence of UTIs will be significantly lower during the treatment period (gentamicin + saline) than during the prior six months.**

In calculating power, we assume that during the study period, there will be a 50% reduction in UTIs from the number that participant experienced during the prior six months, which serves as the control period. These assumptions are based on the findings of a six-month retrospective study of gentamicin. Calculations of power were conducted assuming that paired samples t-tests will be used to assess the first hypothesis. While we may consider using other additional ways of determining differences in UTIs between the baseline and trial periods, paired samples t-tests will be used at least initially. Because we are working with count rather than continuous data, the t-tests will be conducted using natural log-transformed infection rates rather than the raw rates. Based on our assumptions, the sample size needed to have a power of at least 80% will be 15. This is the necessary sample size of participants who complete the study. SPSS version 28 was used to conduct this power analysis.

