### 5.1 INCLUSION CRITERIA

The electronic medical record (EMR) will be pre-screened for all inclusion criteria prior to the baseline interview and initial lab work. Criteria will be confirmed by patient or caregiver report at the screening assessment.

- Provision of signed and dated informed consent form.
- Male or female 18 years or older at time of enrollment.
- History of traumatic SCI or non-traumatic spinal cord disease (SCD), with sustained neurological dysfunction. Traumatic and non-traumatic SCI/D are defined according to the International SCI Standards and Datasets.
- At least 6-months post-initial hospital discharge following SCI/D onset.
- Neurogenic bladder.
- Ability to self-perform daily instillation or with help of others and willingness to adhere to the study regimen.
- Negative pregnancy test (for females of childbearing age) and expresses willing and ability to use appropriate contraception while enrolled in the study.
- History of at least 2 UTIs documented in the EMR during the previous six months (prior to screening).
- Have a designated physician or health care provider for routine urological care who is a member of Michigan Medicine.
- Use of clean intermittent catheterization (CIC) or catheterization through a stoma (i.e. Mitrofanoff) as their primary method of bladder management
- Agreement to adhere to Lifestyle Considerations (see below) throughout participation in the study and to complete the daily dosing log as instructed by the study coordinator.

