### 9.4.2 ANALYSIS OF THE PRIMARY EFFICACY ENDPOINT(S)

To test for significant differences in the incidence of UTIs across periods, as mentioned above, paired samples t-tests will be conducted using log-transformed infection rates rather than the raw rates. We may then subsequently re-analyze this data using a Generalized Linear Mixed Model (GLMM) with log link and a Poisson distribution, as is appropriate for count outcomes data.

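### Protocol and SAP give different primary tests for UTI incidence: the first fails on zero counts, the second states no error method, and the power of 15 completers belongs only to the first

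*Protocol*

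**What the plan says.** Protocol 9.2 sizes the trial on the assumption that "there will be a 50% reduction in UTIs from the number that participant experienced during the prior six months". It says that "paired samples t-tests will be used at least initially", that "the t-tests will be conducted using natural log-transformed infection rates rather than the raw rates", and that "the sample size needed to have a power of at least 80% will be 15", meaning completers. It gives no SD of the paired log differences, no baseline rate and no sidedness.

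Protocol 9.4.2 repeats the method: "paired samples t-tests will be conducted using log-transformed infection rates rather than the raw rates". It then adds an option: "We may then subsequently re-analyze this data using a Generalized Linear Mixed Model (GLMM) with log link and a Poisson distribution". Neither section says what to do with a count of zero.

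Three other places bear on this:
- Section 5.1 requires "History of at least 2 UTIs documented in the EMR during the previous six months".
- Section 9.4.1 says "Missing data will be handled using common statistical methods such as multiple imputation and the estimation maximization approach" and sets significance at 0.05.
- Section 9.3 limits the primary analysis to participants who used the instillations on at least half of the treatment days.

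The SAP (23 June 2023, after protocol version 6.6 of March 2023) has one method for Hypothesis 1. It divides total UTIs by person-time in each period, over all participants, and takes the ratio to the pre-treatment rate. It mentions intervals and p values without a variance formula or model. It justifies the approach briefly by the small sample and the count outcome. It names neither the log t-test nor the mixed model for this hypothesis, and has no sample size or power statement.

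**The concern.** UTI incidence is the only primary endpoint, in a single-arm study of about 15 people. Under the protocol, one participant who stays free of UTIs makes the test impossible to compute as written. Such a participant is also a best responder. A zero is an observed value, so the missing-data rule in 9.4.1 does not cover it. Whoever runs the analysis must invent a rule, and the estimated reduction depends on it.

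Under the SAP the zero problem disappears and two gaps open. Each person contributes counts to both periods, and people may respond differently. The SAP does not say whether its intervals allow for this. The only power statement in either document concerns the other test.

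**Working it through.** **1. The plan's 15.** Inputs from 9.2 and 9.4.1: ratio 0.5, so the effect is ln 2 = 0.693; power 80%; level 0.05; paired t-test. The SD and sidedness are missing, so 15 can only be solved backwards. From the noncentral t with 14 df, 80% power needs a standardised effect of 0.778 two-sided or 0.675 one-sided. The SD of log differences would then be 0.693/0.778 = 0.89, or 0.693/0.675 = 1.03. Two-sided, the required n is 11 at SD 0.7 and 19 at SD 1.0. So 15 is attainable but cannot be checked.

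**2. Chance of a zero.** The baseline mean b is assumed; 5.1 fixes only a floor of 2. With Poisson counts at half of b, P(zero) = exp(-b/2), and P(at least one among 15) = 1 - (1 - exp(-b/2))^15.

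| b | P(zero) per person | At least one in 15 |
|---|---|---|
| 2 | 0.368 | 99.9% |
| 3 | 0.223 | 98% |
| 4 | 0.135 | 89% |
| 5 | 0.082 | 72% |
| 6 | 0.050 | 54% |
| 8 | 0.018 | 24% |

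**3. Effect of the zero rule.** Take one participant who goes from 2 UTIs to 0. Adding a constant c gives a log difference of ln(c/(2+c)): -1.10 for c = 1, -1.61 for c = 0.5, -5.30 for c = 0.01.

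For the whole trial, suppose each baseline is exactly 2 and the true reduction is 50%. Simulation then reads 29% if zeros are dropped, 41% with +1, 53% with +0.5 and 89% with +0.01. This is the extreme case. When the baseline mean is 4 (2 plus a Poisson count), dropping zeros reads 48%.

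The effect on significance depends on the model. With added constants, power is 96-99% at means 2-3 if each observed baseline is the true rate. With independent Poisson periods it is about 40-53% at mean 2 and 51-70% at mean 3.

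**4. The pooled ratio.** Let X and Y be total pre-treatment and on-treatment UTIs over equal days. If all events are treated as Poisson, z = ln(Y/X)/sqrt(1/X + 1/Y). At mean 3, the expected X is 45 and Y is 22.5, so the SE is sqrt(1/45 + 1/22.5) = 0.258. Power is then Φ(0.693/0.258 - 1.96), about 77%. The same formula gives 59% at mean 2 and 87% at mean 4.

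A participant-level alternative uses residuals r_i = y_i - (Y/X)x_i, SE = sqrt(n/(n-1) × Σ r_i²)/Y, and t on 14 df.

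Both were simulated with n = 15, 20,000 trials, two-sided 0.05. Every setting is an assumption:

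| Setting | Pooled Poisson: true null rejected | Participant-level t: power at mean 2 / 3 / 4 |
|---|---|---|
| Observed baseline is the true rate | 0.5% | 78 / 93 / 98% |
| Independent Poisson periods | about 5% | 53 / 72 / 84% |
| Stable rate differing between people (shared gamma frailty) | 4.7-4.8% | 55 / 73 / 83% |
| Independent periods, variance twice the mean | 16% | 32 / 44 / 55% |
| Individual response varies (gamma, variance 1) | 10-25% | not tabulated |

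The participant-level test rejected a true null about 5-7% of the time in these settings. It is not exact everywhere. With strong log-normal variation by person and period (log-SD 1) it reached 8-9%, where the pooled test reached 22-33%.

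The independent-period and shared-frailty settings allow baselines below 2, which 5.1 excludes. The first setting respects that floor.

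**The case against.** The SAP is later, uses a method that handles zeros, and gives a reason. Protocol 9.2 calls the t-test only an initial choice, and the mixed model in 9.4.2 also accepts zeros. If the SAP governs, the zero problem never arises.

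Much of this stands. A count method is a reasonable choice, and the log problem bites only if the protocol test is run and a zero occurs, which becomes less likely at high baselines. But the SAP does not say that it replaces the protocol test. The mixed model is optional and second in order, and its random effects are not described. A random intercept alone, with equal days, returns the pooled ratio and does not allow for varying response. The power statement stays tied to the t-test in every case.

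A reader might infer that differences in UTI frequency between participants make the SAP's p values too small. That does not follow. Stable differences cancel within a person, and the pooled test then holds its level. Only change that varies beyond Poisson inflates it, and the documents give no figure for that. They also do not say that the SAP uses a plain Poisson interval.

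**Conclusion.** The point holds as a failure to reconcile and specify. The two documents name different primary tests. The protocol's test is undefined when a participant has no UTIs, which is likely at baseline means of 2 to 4 and roughly even at 6. The SAP's test has no stated error method. The stated power applies only to the former.

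Two stronger readings are not supported. One is that 15 is too few: under assumed inputs, participant-level power runs from 32% to 98%, so the figure is unverified rather than wrong. The other is that the method was chosen after the data were seen: the SAP's mostly past tense leaves the timing unclear but does not establish it.

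The mismatch between the texts needs no assumptions. Every size given here rests on assumed baseline means and variance models.

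**What to change.** Amend protocol 9.2 and 9.4.2 and the SAP together:
- Drop the log t-test. Name one primary analysis: the treatment versus pre-treatment incidence rate ratio, with log person-time and an interval and p value at participant level. One option is a participant-clustered robust error with t on n-1 df, checked by a sign-flip permutation of the paired rate differences.
- State one primary analysis set, reconciling the half-of-days rule in 9.3 with the SAP's use of all participants, and say which days count as person-time.
- Restate the power of 15 completers for that analysis, with the assumed baseline rate, dispersion and sidedness.
- Label the change post hoc if the data had already been examined when it was made.

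The cost is wording, one simulation and a little more analysis. No extra participants or data are needed. The stated power may be less favourable, and intervals may be wider if participants' responses vary.
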